10.3.1. Definition of AE

AE Definition

• An AE is any untoward medical occurrence in a patient or clinical study participant, temporally associated with the use of study intervention, whether or not considered related to the study intervention.• NOTE: An AE can therefore be any unfavorable and unintended sign (including an abnormal laboratory finding), symptom, or disease (new or exacerbated) temporally associated with the use of study intervention.

Events Meeting the AE Definition

Any abnormal laboratory test results (hematology, clinical chemistry, or urinalysis) or other safety assessments (eg, ECG, radiological scans, vital signs measurements), including those that worsen from baseline, considered clinically significant in the medical and scientific judgment of the investigator (ie, not related to progression of underlying disease). Any abnormal laboratory test results that meet any of the conditions below must be recorded as an AE:
 
Is associated with accompanying symptoms.
 
Requires additional diagnostic testing or medical/surgical intervention.
 
Leads to a change in study dosing (outside of any protocol-specified dose adjustments) or discontinuation from the study, significant additional concomitant drug treatment, or other therapy.
 
• Exacerbation of a chronic or intermittent pre-existing condition including either an increase in frequency and/or intensity of the condition.• New conditions detected or diagnosed after study intervention administration even though it may have been present before the start of the study.• Signs, symptoms, or the clinical sequelae of a suspected drug-drug interaction.• Signs, symptoms, or the clinical sequelae of a suspected overdose of either study intervention or a concomitant medication. Overdose per se will not be reported as an AE/SAE unless it is an intentional overdose taken with possible suicidal/self-harming intent. Such overdoses should be reported regardless of sequelae.• “Lack of efficacy” or “failure of expected pharmacological action” per se will not be reported as an AE or SAE. Such instances will be captured in the efficacy assessments. However, the signs, symptoms, and/or clinical sequelae resulting from

lack of efficacy will be reported as AE or SAE if they fulfil the definition of an AE or SAE.

Events NOT Meeting the AE Definition

- Any clinically significant abnormal laboratory findings or other abnormal safety assessments which are associated with the underlying disease, unless judged by the investigator to be more severe than expected for the participant's condition.
- The disease/disorder being studied or expected progression, signs, or symptoms of the disease/disorder being studied, unless more severe than expected for the participant's condition.
- Medical or surgical procedure (eg, endoscopy, appendectomy): the condition that leads to the procedure is the AE.
- Situations in which an untoward medical occurrence did not occur (social and/or convenience admission to a hospital).
- Anticipated day-to-day fluctuations of pre-existing disease(s) or condition(s) present or detected at the start of the study that do not worsen.

10.3.2. Definition of SAE

If an event is not an AE per definition above, then it cannot be an SAE even if serious conditions are met (eg, hospitalization for signs/symptoms of the disease under study, death due to progression of disease).

A SAE is defined as any untoward medical occurrence that, at any dose:

a. Results in death

b. Is life-threatening

The term 'life-threatening' in the definition of 'serious' refers to an event in which the participant was at risk of death at the time of the event. It does not refer to an event, which hypothetically might have caused death, if it were more severe.

c. Requires inpatient hospitalization or prolongation of existing hospitalization

In general, hospitalization signifies that the participant has been detained (usually involving at least an overnight stay) at the hospital or emergency ward for observation and/or treatment that would not have been appropriate in the physician's office or outpatient setting. Complications that occur during hospitalization are AEs. If a complication prolongs hospitalization or fulfills any other serious criteria, the event is serious. When in doubt as to whether "hospitalization" occurred or was necessary, the AE should be considered serious.

Hospitalization for elective treatment of a pre-existing condition that did not worsen from baseline is not considered an AE.

d. Results in persistent disability/incapacity

- The term disability means a substantial disruption of a person's ability to conduct normal life functions.
- This definition is not intended to include experiences of relatively minor medical significance such as uncomplicated headache, nausea, vomiting, diarrhea, influenza, and accidental trauma (eg, sprained ankle) which may interfere with or prevent everyday life functions but do not constitute a substantial disruption.

e. Is a congenital anomaly/birth defect

f. Other situations:

- Medical or scientific judgment should be exercised in deciding whether SAE reporting is appropriate in other situations such as important medical events that may not be immediately life-threatening or result in death or hospitalization but may jeopardize the participant or may require medical or surgical intervention to prevent one of the other outcomes listed in the above definition. These events should usually be considered serious.
 - Examples of such events include invasive or malignant cancers, intensive treatment in an emergency room or at home for allergic bronchospasm, blood dyscrasias or convulsions that do not result in hospitalization, or development of drug dependency or drug abuse.
- Suspected transmission via a Pfizer product of an infectious agent, pathogenic or non-pathogenic, is considered serious. The event may be suspected from clinical symptoms or laboratory findings indicating an infection in a participant exposed to a Pfizer product. The terms "suspected transmission" and "transmission" are considered synonymous. These cases are considered unexpected and handled as serious expedited cases by pharmacovigilance personnel. Such cases are also considered for reporting as product defects, if appropriate.
- In this study, the following events that occur poststudy treatment infusion are considered medically important events and should be reported as SAEs:
 1. Any participant develops clinical thrombotic event (with the exception of IV infusion-site thrombophlebitis).
 2. Any participant develops a confirmed FVIII inhibitor.
 3. Any participant develops clinically significant hypersensitivity reaction (eg, bronchospasm and anaphylaxis). Infusion related reactions should be reported as serious only if they meet serious criteria.

4. Any participant develops a hepatic malignancy.
5. Any participant develops drug-related elevated hepatic transaminases that fail to improve or resolve through treatment with immunosuppressive regimens.
6. Any occurrence of a malignancy assessed as having reasonable possibility relatedness to study drug.

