
Estimate the durability of efficacy up to 5 years after PF-07055480 infusion.	
The following parameters will be analyzed yearly or by visit as appropriate:
 
ABR.FVIII activity level.AIR of exogenous FVIII.Annualized FVIII consumption.ABR of specific type:
by cause (spontaneous or traumatic).by location (in joint, in target joints, or in soft tissue).Total ABR.Total ABR by cause and by location.Percentage of participants without bleeds.Change from baseline in joint health as measured by the HJHS instrument.Change from baseline in PRO endpoints: Haem-A-QoL and HAL. 
In addition, ABR, Total ABR, and AIR will be analyzed throughout the 5-year study period.

Secondary Safety Objectives	Secondary Safety Endpoints

To estimate the safety and tolerability of PF-07055480, including immunogenicity, for the study duration of 5 years after PF-07055480 infusion.	
Incidence and severity of AEs.Events of special interest (such as hypersensitivity reactions, clinically reported thrombotic events, and malignancy).Immunogenicity:
Antibodies against AAV6 capsid protein (nAbs and ADAs).

	
○ T-cell responses against AAV6 capsid and against the transgene.○ FVIII inhibitors.
--	---

Overall Design

C3731003 is a pivotal Phase 3 study to evaluate the clinical efficacy and safety of a single IV infusion of PF-07055480 in adult male participants with moderately severe or severe hemophilia A (FVIII:C \leq 1%) for the study duration of 5 years. The study will enroll eligible participants who were followed on routine prophylaxis with FVIII products in the non-IMP lead-in Study C0371004. After this 5-year follow-up period in Study C3731003, participants will be invited to enter a separate study to assess the long-term safety and effectiveness of PF-07055480 for the treatment of hemophilia A for a total of up to 10 additional years, corresponding to up to 15 years post-PF-07055480 infusion.

Disclosure Statement

This is a Single Group Treatment study with 1 Arm that has No masking.

Number of Participants

Approximately 70 participants from the lead-in Study C0371004 will be enrolled to achieve at least 50 dosed participants completing at least 15 months of follow-up postinfusion.

Study population

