8.2.5. Samples for Other Vector Integration Related Testing (if applicable)

In the event that certain findings occur (for example, new abnormalities), further testing may be done as standard of care; for example, repeat testing over time may be ordered. To investigate an abnormal finding, an investigator may recommend a biopsy or tissue collection (liver or other location). In this event, tissue obtained may be requested by the sponsor for further analyses. Tissue analyses may be helpful in establishing (or refuting) a relationship between the adverse event and the gene transfer vector. Analyses would include a vector integration analysis, and possibly quantitation of vector transgene expression, depending on tissue integrity and viability. The consent includes tissue collection; surgical and procedural consents generally cover obtaining samples of tissue for analyses. Likewise, if autopsy material became available for analysis of attribution of vector to an adverse event, tissue would be requested by the sponsor to assess this possibility.

Refer to [Section 8.1.5.1](#) for the management of incidental findings.

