8.3.1. Time Period and Frequency for Collecting AE and SAE Information

All ongoing AEs and SAEs in the lead-in study (C0371004), including events of special interest, as defined in the lead-in study (C0371004), will be collected as medical history for this study. Historical data on Medical, Surgical and Hemophilia History will be captured from the lead-in study. Any new AEs/SAEs after completion of the lead-in study will follow the AE reporting process ([Appendix 3](#)).

The time period for actively eliciting and collecting AEs and SAEs (“active collection period”) for each participant begins from the time the participant provides informed consent, which is obtained before the participant's participation in the study (ie, before undergoing any study-related procedure and/or receiving study intervention), through and including a minimum of 5 years after the last administration of the study intervention, or at EOS for participants who discontinue. The active collecting period for this study is categorized into short-term or long-term monitoring period and is defined later in this section.

For participants who are screen failures, the active collection period ends when screen failure status is determined.

Follow-up by the investigator continues throughout and after the active collection period and until the AE or SAE or its sequelae resolve or stabilize at a level acceptable to the investigator, and Pfizer concurs with that assessment.

During the short-term monitoring period (up to and including 104 weeks postinfusion) all SAEs (including medically important events, [Appendix 3](#)) and AEs will be collected.

During the long-term monitoring period (Week 105 postinfusion to EOS) the following AEs will be collected:

- SAEs (including medically important events, [Appendix 3](#))
- Nonserious AEs determined to be related to study intervention by the investigator or where causality is unknown.

Investigators are not obligated to actively seek AEs or SAEs after conclusion of the study participation. However, if the investigator learns of any SAE, including a death, at any time after a participant has been discharged from the study, and he/she considers the event to be reasonably related to the study intervention or study participation, the investigator must promptly notify the sponsor.

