8.3.8. Adverse Events of Special Interest

Adverse events of special interest (AESIs) are examined as part of routine safety data review procedures throughout the clinical trial and as part of signal detection processes.

All AESIs must be reported as an AE or SAE following procedures described in [Sections 8.3.1](#) through [8.3.4](#). An AESI is to be recorded as an AE or SAE on the CRF. In addition, an AESI that is also an SAE must be reported using the CT SAE Report Form.

Adverse events of special interest include: all medically important events (see [Appendix 3](#)) that are to be reported as an SAE, and any clinical thrombotic event or hypersensitivity/infusion-related reactions events assessed as non-serious AEs.

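### Malignancy is an unconditional event-of-special-interest endpoint, but a non-hepatic malignancy counts as one only if judged related to study drug

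*Protocol*

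**What the plan says.** **Endpoint.** The secondary safety endpoints include "Events of special interest (such as hypersensitivity reactions, clinically reported thrombotic events, and malignancy" (Protocol Section 1.1, repeated in Protocol Section 3 and SAP Section 2.2, Table 2). Malignancy carries no qualifier for site, seriousness or causality.

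**Operational definition.** Protocol Section 8.3.8 begins "Adverse events of special interest include: all medically important events". It refers to Appendix 3, limits these to events that must be reported as SAEs, and adds thrombotic and hypersensitivity or infusion-related events even when they are non-serious. It does not mention malignancy separately.

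**The list.** Protocol Section 10.3.2 gives six numbered post-infusion events that "are considered medically important events and should be reported as SAEs". Two concern cancer. Item 4 is "Any participant develops a hepatic malignancy", with no causality condition. Item 6 is "Any occurrence of a malignancy assessed as having reasonable possibility relatedness to study drug".

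**General text.** Earlier in the same section, the general passage on important medical events says "Examples of such events include invasive or malignant cancers". Such events should usually be treated as serious, and causality is not a condition.

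**Collection.** Protocol Section 8.3.1 collects all AEs and SAEs through Week 104. From Week 105 it collects SAEs and "Nonserious AEs determined to be related to study intervention by the investigator or where causality is unknown". The Schedule of Activities, the Section 10.3.3 table and SAP Section 3.5.1 repeat this.

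**Reporting.** SAP Section 6.6.1 summarises all serious AEs and, separately, events of special interest, for both the short-term and long-term monitoring periods. It does not define the latter.

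**The concern.** The endpoint promises a count of malignancies. The definition behind it delivers all hepatic malignancies plus those others that an investigator attributes to the vector. In a single-arm, unmasked trial there is no concurrent group against which a causality opinion can be calibrated, so the interpretable quantity is the unconditional count, with attribution shown beside it.

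The attribution test is also demanding. Protocol Section 10.3.3 says a reasonable possibility needs facts, evidence or arguments pointing to causation; being unable to exclude a link is not enough. For a non-hepatic cancer a site will have little to go on. The insertional-mutagenesis entry of the risk assessment (Section 2.3.1) says no adequate animal model exists for tumorigenic potential, and that vector genomes were detected outside the liver, though at much lower levels.

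The label has consequences. Section 8.3.8 says these events feed routine safety review and signal detection, and Section 9.5.1 gives events of special interest as an example of what may prompt an ad hoc eDMC meeting. The long-term follow-up study described in Section 4.1 lists malignancy as an event of special interest without condition, so counts from the two studies might not be comparable.

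**Working it through.** The plan states no figure for this point, so the check is to follow each type of malignancy through the definitions.

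**Which list does Section 8.3.8 point to?** It refers to medically important events in Appendix 3 that are to be reported as SAEs. The six-item list in Section 10.3.2 is introduced in nearly the same terms, and the Section 10.3.3 table also speaks of medically important events as defined in Section 10.3.2. The natural reading is therefore the six-item list.

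**Applying it:**

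| Malignancy | Event of special interest? | In SAE tables? | Collected to Week 104? | Collected after Week 104? |
|---|---|---|---|---|
| Hepatic, any causality | Yes (item 4) | Yes | Yes | Yes |
| Non-hepatic, judged related | Yes (item 6) | Yes | Yes | Yes |
| Non-hepatic, causality unknown | Yes, if handled as related (Section 10.3.3) | Yes, if handled as related | Yes | Yes |
| Non-hepatic, serious, judged unrelated | **No** | Yes | Yes | Yes |
| Non-hepatic, non-serious, judged unrelated | **No** | No; general AE tables only | Yes | **No** |

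Only the last two rows are affected. The fourth loses its place in the special-interest table. The fifth loses that and, from Week 105, is not recorded.

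**Comparison with the other named events.** The endpoint names three types. Section 8.3.8 extends thrombotic and hypersensitivity or infusion-related events to non-serious cases with no causality test. Non-hepatic malignancy is the only named type that must pass one.

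**Size of one judgement.** Section 9.2 plans about 70 enrolled, to give at least 50 dosed with 15 months of follow-up. One event moves the reported incidence by 1/70 = 1.4 percentage points, or 1/50 = 2.0 points if only 50 are dosed.

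**Length of the collection gap.** Planned follow-up is 260 weeks. The gap covers 260 − 104 = 156 weeks, and 156/260 = 60% of follow-up.

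**Can the fifth row occur?** Exclusion criterion 5 admits participants with adequately treated basal or squamous cell skin cancer, so a further non-serious skin cancer during follow-up is plausible. The documents give no rate.

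**The case against.** The strongest reply is that little information disappears. Invasive cancers should usually be serious under the general text of Section 10.3.2, all SAEs are collected to end of study, and SAP Section 6.6.1 tabulates them for both periods. A cancer judged unrelated would be missing from one table and present in the next. This stands, and it limits the point.

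A second reply is that Section 8.3.8 does not expressly confine itself to the six items, so the general cancer example could be read in. That is possible. But items 4 and 6 would then be largely redundant, and the text would still need clarifying.

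Third, an independent eDMC meets about every six months, causality can be revised on follow-up, and a footnote in SAP Section 6.6.1 discloses the two-year limit on non-serious unrelated events. These soften the consequence but do not align the definition with the endpoint.

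Three stronger readings are tempting, and the documents do not support them:

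- *That insertional-mutagenesis risk as a whole is counted through an open-label opinion.* Section 2.3.1 places the greatest integration potential in hepatocytes, and hepatic malignancy is counted regardless of causality, with ultrasound and α-fetoprotein monitoring at least yearly.
- *That the order is circular, because relatedness must be judged before the tissue that would inform it is studied.* Section 8.2.5 says "Tissue analyses may be helpful in establishing (or refuting) a relationship between the adverse event and the gene transfer vector", but the trigger for requesting tissue is an abnormal finding, not special-interest status.
- *That the defect can be sized as the chance of a cancer in 70 × 5 = 350 person-years.* An assumed 0.1 to 0.5 cancers per 100 person-years gives 0.35 to 1.75 expected and, by 1 − exp(−expected), a 30% to 83% chance of at least one. The documents give no rate. The sum assumes all 70 are dosed and followed for five years, and it counts hepatic, related and unknown-causality cancers that the plan already captures. It does not estimate the filtered subset.

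**Conclusion.** The mismatch is real and narrow. A safety endpoint named without condition is put into practice, for non-hepatic malignancy only, through a causality opinion in an unmasked single-arm trial, and the SAP inherits that filter without comment. The loss has two parts: the special-interest count, and non-serious malignancies judged unrelated from Week 105 onward, which are never recorded. Serious cancers are not lost from the safety data.

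The conclusion rests on reading Section 8.3.8 as pointing to the six-item list, which its wording favours but does not compel, and on unknown causality being handled as related when events are classified. The number of affected cases cannot be estimated from the documents. This is a cheap improvement, not a flaw in the overall safety plan.

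**What to change.** 1. **Protocol Section 8.3.8:** add to the definition *any malignancy, regardless of site, seriousness or causality*.
2. **Protocol Section 8.3.1**, with the Schedule of Activities and the Section 10.3.3 table: require all malignancies to be collected through end of study. SAP Section 3.5.1 repeats the collection rule and should follow.
3. **SAP Section 6.6.1:** define the malignancy event of special interest in the same words, and show investigator causality as a separate column.

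Leave item 6 of Section 10.3.2 as the SAE-reporting rule. Everything in that list is to be reported as an SAE, so removing the seriousness and causality conditions there would make every skin cancer an SAE.

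The cost is a few lines of text, one category in the safety outputs, and a few extra records of background cancers. No new procedure or visit is needed.

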10.3.3. Recording and Follow-Up of AE and/or SAE

AE and SAE Recording/Reporting		
The table below summarizes the requirements for recording adverse events on the CRF and for reporting serious adverse events on the CT SAE Report Form to Pfizer Safety. These requirements are delineated for 3 types of events: (1) SAEs; (2) non-serious adverse events (AEs); and (3) exposure to the investigational product under study during pregnancy and occupational exposure.		
It should be noted that the CT SAE Report Form for reporting of SAE information is not the same as the AE page of the CRF. When the same data are collected, the forms must be completed in a consistent manner. AEs should be recorded using concise medical terminology and the same AE term should be used on both the CRF and the CT SAE Report Form for reporting of SAE information.		
During the Short Term Monitoring Period (up to and including 104 weeks postinfusion)		
Safety Event	Recorded on the CRF	Reported on the CT SAE Report Form to Pfizer Safety Within 24 Hours of Awareness
SAE (including the medically important events – as defined in Section 10.3.2)	All	All
Non-serious AE	All	None
Exposure to the study intervention under study during pregnancy and occupational exposure	All AEs/SAEs associated with exposure during pregnancy. Occupational exposure is not recorded.	All (and EDP supplemental form for EDP) Note: Include all SAEs associated with exposure during pregnancy. Include all AEs/SAEs associated with occupational exposure.

During the Long Term Monitoring Period (Week 105 until EOS Visit)

Safety Event	Recorded on the CRF	Reported on the CT SAE Report Form to Pfizer Safety Within 24 Hours of Awareness
SAE (including the medically important events – as defined in Section 10.3.2)	All	All
Non-serious AE determined to be related to the study intervention by the investigator; and/or where causality is unknown.	All	None
Exposure to the study intervention under study during pregnancy and occupational exposure	All AEs/SAEs associated with exposure during pregnancy. Occupational exposure is not recorded.	All (and EDP supplemental form for EDP) Note: Include all SAEs associated with exposure during pregnancy. Include all AEs/SAEs associated with occupational exposure.

- When an AE/SAE occurs, it is the responsibility of the investigator to review all documentation (eg, hospital progress notes, laboratory reports, and diagnostics reports) related to the event.
- The investigator will then record all relevant AE/SAE information in the CRF.
- It is **not** acceptable for the investigator to send photocopies of the participant's medical records to Pfizer Safety in lieu of completion of the CT SAE Report Form/AE/SAE CRF page.
- There may be instances when copies of medical records for certain cases are requested by Pfizer Safety. In this case, all participant identifiers, with the exception of the participant number, will be redacted on the copies of the medical records before submission to Pfizer Safety.
- The investigator will attempt to establish a diagnosis of the event based on signs, symptoms, and/or other clinical information. Whenever possible, the diagnosis (not the individual signs/symptoms) will be documented as the AE/SAE.

Assessment of Intensity

The investigator will make an assessment of intensity for each AE and SAE reported during the study and assign it to 1 of the following categories:
 
 • Mild: An event that is easily tolerated by the participant, causing minimal discomfort and not interfering with everyday activities. • Moderate: An event that causes sufficient discomfort and interferes with normal everyday activities. • Severe: An event that prevents normal everyday activities. An AE that is assessed as severe should not be confused with a SAE. Severe is a category utilized for rating the intensity of an event; and both AEs and SAEs can be assessed as severe. 
An event is defined as ‘serious’ when it meets at least 1 of the predefined outcomes as described in the definition of an SAE, NOT when it is rated as severe.

Assessment of Causality

 • The investigator is obligated to assess the relationship between study intervention and each occurrence of each AE/SAE. • A “reasonable possibility” of a relationship conveys that there are facts, evidence, and/or arguments to suggest a causal relationship, rather than a relationship cannot be ruled out. • The investigator will use clinical judgment to determine the relationship. • Alternative causes, such as underlying disease(s), concomitant therapy, and other risk factors, as well as the temporal relationship of the event to study intervention administration will be considered and investigated. • The investigator will also consult the Investigator’s Brochure and/or Product Information, for marketed products, in his/her assessment. • For each AE/SAE, the investigator must document in the medical notes that he/she has reviewed the AE/SAE and has provided an assessment of causality. • There may be situations in which an SAE has occurred and the investigator has minimal information to include in the initial report to the sponsor. However, it is very important that the investigator always make an assessment of causality for every event before the initial transmission of the SAE data to the sponsor. • The investigator may change his/her opinion of causality in light of follow-up information and send a SAE follow-up report with the updated causality assessment. • The causality assessment is one of the criteria used when determining regulatory reporting requirements. • If the investigator does not know whether or not the investigational product caused the event, then the event will be handled as “related to investigational product” for reporting purposes, as defined by the sponsor” and "In addition, if the investigator

determines that an SAE is associated with study procedures, the investigator must record this causal relationship in the source documents and CRF, and report such an assessment in the dedicated section of the CT SAE Report Form and in accordance with the SAE reporting requirements.

Follow-up of AEs and SAEs

- The investigator is obligated to perform or arrange for the conduct of supplemental measurements and/or evaluations as medically indicated or as requested by the sponsor to elucidate the nature and/or causality of the AE or SAE as fully as possible. This may include additional laboratory tests or investigations, histopathological examinations, or consultation with other health care professionals.
- If a participant dies during participation in the study or during a recognized follow-up period, the investigator will provide Pfizer Safety with a copy of any postmortem findings including histopathology.
- New or updated information will be recorded in the originally completed CRF.
- The investigator will submit any updated SAE data to the sponsor within 24 hours of receipt of the information.

